Re-screening in general is not allowed, however patients enrolled in the registry may qualify for a re-screening opportunity at the discretion of the investigator. For more details on the registry of first-degree family members of patients with MS, see Appendix 4.

In the case of a clinical neurologic event consistent with CNS demyelination, the patient should have an unscheduled visit and a full assessment, as detailed in the SOA. Upon confirmation of a clinical relapse, the patient will be discontinued from the study and should start commercially available DMT, including ocrelizumab, at the discretion of the treating physician. In the event of radiologic progression, in which a new lesion suggestive of MS develops, the choice to continue or discontinue from the study in order to initiate treatment is at the discretion of the treating physician.

Treatment may be stopped at any time due to lack of clinical benefit, unacceptable toxicity, withdrawal of consent, patient or physician decision to discontinue treatment, death, or if the sponsor decides to close the trial, whichever occurs first.

[figure not shown]
An external, independent DMC (iDMC) will periodically review safety data throughout the study until the primary analysis is performed. Following unblinding, iDMC involvement in safety monitoring is no longer needed. Analyses required for the iDMC data review will be performed as described in the iDMC Charter.

All patients enrolled into the main study will be evaluated for safety throughout the study. In the case of early termination, the patient will be asked to return for an early termination visit.

Patients who do not meet the criteria for participation in this study (screen failure) may qualify for one re-screening opportunity (for a total of two screenings per participant) at the investigator's discretion. The investigator will record reasons for screen failure in the screening log. Family members who undergo radiologic pre-screening and do not have lesions meeting DIS criteria are not considered screen failures and will be enrolled in the family registry.

[Figure 1](#) presents an overview of the study design. A schedule of activities is provided in [Appendix 1](#).

Figure 1 Study Schema

Tx=treatment; * = primary endpoint is event driven therefore patients may be unblinded after reaching primary endpoint

Confidential — For internal use only. Do not copy, distribute or use without prior written consent.

1

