prior to initiation of study drug or ongoing therapy (e.g., physiotherapy) to the study completion/discontinuation visit. All such medications and therapies (including their indication) should be reported to the investigator and recorded on the appropriate eCRF.

Treatment of First Clinical Neurologic Event

In the case of the development of an acute or progressive clinical neurologic event consistent with CNS demyelination during study, the patients should have an unscheduled visit and a full assessment, as detailed in the SOA. As described in Section 4.5.12 a neurologic event consistent with CNS demyelination for this study is defined as the occurrence of new and/or worsening neurological symptoms suggestive of MS that persist for >24 hours and should not be attributable to confounding clinical factors (e.g., fever, infection, injury, adverse reactions to medications). In the case of an acute syndrome, it should be immediately preceded by a stable or improving neurological state for least 30 days. In some rare cases a progressive clinical syndrome (e.g., leg weakness, cognitive impairment, EDSS worsening) may develop with a temporal profile revealing at least 12-months of neurologic deficit as per the treating physician's judgement. The new or worsening neurological symptoms must be adjudicated by a Sponsor-appointed adjudication committee, comprised of three expert neuroimmunology clinicians, who will review documentation associated with the event and confirm whether a relapse has occurred. Confirmed relapses will contribute to the primary endpoint.

The patient may receive treatment with IV or oral corticosteroids, if judged to be clinically appropriate by the investigator. The following standardized treatment regimen may be used as warranted: 1 g/day IV methylprednisolone for a maximum of 5 consecutive days. In addition, at the discretion of the investigator, corticosteroids may be stopped abruptly or tapered over a maximum of 10 days. After a confirmed clinical relapse, patients will be discontinued from the study and start commercially available DMT approved for MS, including ocrelizumab, at the discretion of the treating physician. Whether patients continue or discontinue the treatment based on the occurrence of a neurologic event consistent with MS is at the discretion of the treating physician and the patient, and whether the patient or investigator feels he or she has met the criteria for withdrawal.

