Treatment may be stopped at any time due to lack of clinical benefit, unacceptable toxicity, withdrawal of consent, patient or physician decision to discontinue treatment, death, or if the sponsor decides to close the trial, whichever occurs first.

Treatment of Radiologic Event

In the event of radiologic progression, in which a new contrast-enhancing or T2-weighted lesion suggestive of MS develops, the choice to continue or discontinue from the study

in order to initiate treatment with a DMT, including commercial OCREVUS®, is at the discretion of the treating physician. If a commercial disease modifying therapy is initiated, the participant will be discontinued from all study-related treatments.

Regardless of whether the participant is started on commercial disease modifying therapy, individuals with a radiologic event should complete study assessments until they have completed week 208 or until they have had a confirmed clinical relapse, whichever occurs first.

As described above in Section 4.4.1 treatment may be stopped at any time due to lack of clinical benefit, unacceptable toxicity, withdrawal of consent, patient or physician decision to discontinue treatment, death, or if the sponsor decides to close the trial, whichever occurs first.

Prohibited Therapy

The following therapies for MS are not permitted during the treatment portion of the study (through week 72): Other B-cell targeted therapies (e.g., rituximab, atacicept, belimumab, or ofatumumab, etc.), natalizumab, fingolimod, siponimod, alemtuzumab, daclizumab, cladribine, teriflunomide, dimethyl fumarate, diroximel fumarate, ozanimod, interferons, glatiramer acetate, cyclophosphamide, mitoxantrone, azathioprine, mycophenolate mofetil, cyclosporine, methotrexate, total body irradiation, bone marrow transplantation, IV Ig, plasmapheresis, other approved or investigational therapies for MS.

After patients have completed (or discontinued) treatment with study drug, they may receive alternative treatment for MS as judged clinically appropriate by the investigator. However, as sufficient data are not available regarding risks associated with switching to other products, the following recommendations are given:

Caution is advised if patients remain B-cell depleted.

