RBR samples will be tracked in a manner consistent with Good Clinical Practice by a quality-controlled, auditable, and appropriately validated laboratory information management system, to ensure compliance with data confidentiality as well as adherence to authorized use of samples as specified in this protocol and in the Informed Consent Form. Sponsor monitors and auditors will have direct access to appropriate parts of records relating to patient participation in the RBR for the purposes of verifying the data provided to the Sponsor. The site will permit monitoring, audits, IRB/EC review, and health authority inspections by providing direct access to source data and documents related to the RBR samples.

TREATMENT, PATIENT, AND STUDY DISCONTINUATION

Study Treatment Discontinuation

Patients must permanently discontinue study treatment if they experience any of the following:

Any medical condition that the investigator or Sponsor determines may jeopardize the patient's safety if he or she continues to receive study treatment

Investigator or Sponsor determination that treatment discontinuation is in the best interest of the patient

Additionally, patients must be withdrawn from treatment under the following circumstances:

Life-threatening (National Cancer Institute Common Terminology Criteria for Adverse Events [NCI CTCAE] Grade 4) infusion-related event that occurred during a previous ocrelizumab infusion

Demonstrate active hepatitis B infection, either new onset or reactivation

PML

Newly diagnosed malignancy

Patients who become pregnant /or lactating

Patients who decide to discontinue treatment

The primary reason for study treatment discontinuation should be documented on the appropriate eCRF. Patients who discontinue study treatment prematurely will not be replaced.

If a patient meets any of the treatment withdrawal criteria (see above), the patient must be withdrawn from treatment. Patients who prematurely withdraw from study drug treatment will need to return to the clinic for an unscheduled treatment discontinuation visit (see Appendix 1 for additional details). After treatment discontinuation, every effort should be made to have the patient enter the follow-up phase of the study.

For patients who have withdrawn from study drug treatment, the investigator should decide as to further treatment of the underlying disease (see Section 4.4 for recommendations on alternative treatments for MS post-ocrelizumab).

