Based on additional patient exposure an association between decrease in immunoglobulins and serious infections with ocrelizumab treatment was observed and was most apparent for IgG. There was no difference in the pattern (type, latency, duration, outcome) of the serious infections reported in this subset of patients compared to the overall serious infections profile. In addition, risk factors for a subset of patients at higher risk of serious infections could not be identified.

Delayed Return of Peripheral B Cells

Treatment with ocrelizumab leads to rapid depletion of CD19+ B cells in blood by 14 days posttreatment (first timepoint of assessment) as an expected pharmacologic

effect. This was sustained throughout the treatment period. The longest follow-up duration after the last ocrelizumab infusion from Phase II Study WA21493 in 51 patients indicates that the median time to repletion (returned to baseline/LLN, whichever occurred first) of B cells was 72 weeks (range 27–175 weeks). Patients with prolonged B-cell depletion should be monitored until his or her B cells have repleted.

Potential Risks

Progressive Multifocal Leukoencephalopathy

It has been reported in patients receiving ocrelizumab but only in patients where other contributory factors were present, such as prior immunosuppressive treatment (for example natalizumab or fingolimod). Physicians should be vigilant for early signs and symptoms of PML, which can include any new onset, or worsening of neurological signs or symptoms as these can be similar to an MS relapse. If PML is suspected, dosing with ocrelizumab must be withheld. Evaluation of PML, including MRI, confirmatory CSF testing for JC Viral DNA and repeat neurological assessments, should be considered. If PML is confirmed, ocrelizumab must be discontinued permanently.

Refer to Appendix 7 for guidance for diagnosis of PML. Please see the Ocrelizumab Investigator's Brochure for more details.

Hypersensitivity Reactions

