The primary efficacy endpoint for this study is to evaluate the efficacy of ocrelizumab compared with placebo on delaying the time to development of new radiological or clinical evidence of MS, defined as the time from baseline to first new T1 gadolinium-enhancing lesions and/or new or enlarging T2 lesions consistent with MS OR first clinical evidence of MS, i.e., neurological event resulting from CNS demyelination as evidenced by acute or progressive clinical syndrome consistent with MS.

The time to development of radiological or clinical evidence of MS in the ocrelizumab arm and placebo arm will be compared and tested using a stratified log-rank test with the null and alternative hypotheses as follows:

H_0 : There is no difference in the time to onset of radiological or clinical evidence of MS between the ocrelizumab and placebo groups.

H_1 : There is a difference in the time to onset of radiological or clinical evidence of MS between the ocrelizumab and placebo groups.

The proportion of patients with radiological or clinical evidence of MS over time will be estimated using Kaplan-Meier methodology and the overall hazard ratio will be estimated using a stratified Cox proportional hazards model. In the presence of a large amount of interval censoring, stratified generalized log rank test and stratified proportional hazards model with full likelihood function will be used to compare survival between groups.

Estimands for the Primary Analysis

The primary analysis has a treatment-policy estimand (see ICH E9[R1] 2019) on the basis of the following attributes:

Population: All randomized patients.

Variable: Time from baseline to development of new radiological or clinical evidence of MS.

Intercurrent events:

Withdrawal from treatment: Patients will be followed until the primary analysis regardless of adherence to study treatment or reason for treatment withdrawal. Data will continue to be collected from such patients and included in the analysis, following a treatment-policy strategy.

Initiation of another MS therapy: Data will continue to be collected from such patients and included in the analysis, following a treatment-policy strategy.

Patients still ongoing and without an initial evidence of MS event at the time of study unblinding will be censored at the date of the last assessment.

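### Sections 3.1 and 4.4.2 let a patient with a new lesion leave the study, while a later rule in 4.4.2 keeps that patient in assessments; footnotes c and r disagree on the exit MRI

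*Combined protocol and SAP*

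**What the plan says.** **New lesion.** Section 3.1 (Description of the Study) says of radiologic progression that "the choice to continue or discontinue from the study in order to initiate treatment is at the discretion of the treating physician". Section 4.4.2 (Treatment of Radiologic Event) opens in the same way: if a "new contrast-enhancing or T2-weighted lesion suggestive of MS develops, the choice to continue or discontinue from the study" to begin a DMT again rests with the treating physician. Its next sentence says that starting a commercial DMT ends study-related treatments; it does not say that participation ends. The rule after that covers every such patient, on a commercial DMT or not: "individuals with a radiologic event should complete study assessments until they have completed week 208 or until they have had a confirmed clinical relapse", whichever is first.

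**Related passages.** Section 4.6.1 says: "After treatment discontinuation, every effort should be made to have the patient enter the follow-up phase of the study". The primary estimand in Section 6.4.1 says: "Initiation of another MS therapy: Data will continue to be collected from such patients and included in the analysis, following a treatment-policy strategy". Section 6.4.1 also censors a patient who withdraws from the study. Section 6.4.2 gives the secondary estimands the primary analysis's population and missing-data handling, but names no strategy for DMT start. It analyses the continuous secondary endpoints by MMRM under MAR and promises sensitivity analyses of that assumption.

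**Exit MRI.** In Appendix 1 the Study Completion/Early Termination column carries footnote c: every assessment is mandatory, and MRI is excused only if one was done in the previous 8 weeks. The brain and cervical-spine MRI cells in that column carry footnote r: the scan is optional and tied to an actual or suspected neurologic event.

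**The concern.** A site can follow the discretion in Section 3.1 to the letter and so break the later rule in Section 4.4.2. No text says which prevails.

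All six secondary endpoints (two lesion counts, T2 volume, brain volume, cord volume and sNfL) are read at Weeks 48, 104 and 208. The patients who could leave are those whose disease has just shown activity, so their later values would be missing for a reason tied to the outcome. In the extreme case where every such patient left, the Week 208 data would contain nobody with a new lesion on an earlier scheduled scan, in either arm.

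The footnote conflict has a different consequence. A patient who drops out without an event may or may not be scanned on leaving, and that scan could show a first primary event.

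**Working it through.** The plan gives no figure for this point, so the check compares the text and then sizes the consequence.

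**Text.** Both discretion clauses speak of leaving the study. One could read that as stopping study treatment, but Section 4.4.2 uses a separate expression for study-related treatments, and Sections 4.6.1 and 4.6.2 treat stopping treatment and leaving the study as different things. A site that keeps every such patient in assessments complies with all the passages; a site that uses the discretion as written does not. For the exit MRI, both footnotes govern the same cell and give different answers.

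**Inputs** (Section 6.1): events by 4 years in 33% (placebo) and 20% (ocrelizumab); 10% annual dropout; about 100 patients randomised 1:1, taken as 50 per arm. Assumed here: constant hazards, dropout independent of events, 52-week years.

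- Event hazard h = −ln(1 − p)/4: placebo 0.1001, ocrelizumab 0.0558 per year.
- Dropout hazard d = −ln(0.9) = 0.1054 per year.

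**First events while still in the study** = 50 × h/(h + d) × (1 − 0.9⁴(1 − p)):
- Placebo: 50 × 0.4872 × 0.5604 = 13.7.
- Ocrelizumab: 50 × 0.3462 × 0.4751 = 8.2.
- Total 21.9, close to the approximately 21 events planned. Placebo share 13.7/21.9, about 62%.

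**Patients still followed.** If event patients stay, the number is 50 × 0.9^t per arm; if all leave, 50 × 0.9^t × (1 − p)^(t/4).

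| | Event patients stay (per arm) | All leave: placebo | All leave: ocrelizumab |
|---|---|---|---|
| 2 years (about Week 104) | 40.5 | 33.2 | 36.2 |
| 4 years (about Week 208) | 32.8 | 22.0 | 26.2 |

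At 4 years the difference is 10.8 placebo and 6.6 ocrelizumab patients. This is an upper bound at the planning rates: the documents do not split radiologic from clinical events, and a confirmed relapse ends assessments under either rule.

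**Exit MRI.** Scheduled scans are at screening (taken as Week 0) and Weeks 24, 48, 72, 104, 156 and 208. Event-free dropouts by Week 208 = 50 × d/(h + d) × (1 − 0.9⁴(1 − p)), which is 14.4 placebo and 15.5 ocrelizumab.

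Two sums over the scan intervals from a to b, in years, give those who drop out more than 8 weeks after a scan:
- Event-free at the last scan: 50 × e^(−ha) × [e^(−d(a + 8/52)) − e^(−db)]. For placebo between Weeks 104 and 156 this is 50 × 0.8185 × (0.7970 − 0.7290) = 2.8. Over all intervals: 11.1 placebo, 11.9 ocrelizumab.
- Still event-free at exit: 50 × d/(h + d) × [e^(−(h+d)(a + 8/52)) − e^(−(h+d)b)]. Over all intervals: 10.6 placebo, 11.6 ocrelizumab.

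By either count this is about 11 placebo and 12 ocrelizumab patients. The differences, 0.47 and 0.29 before rounding, are first events expected between the last scan and exit: about 0.8 in total. That figure assumes every such patient attends the exit visit, and it includes clinical events that would be seen without a scan.

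**The case against.** The strongest defence is that Section 4.4.2 largely settles the matter. Its middle sentence ends only study treatments, its next rule applies regardless of DMT use, Section 3.1 is a summary, and Sections 4.6.1 and 6.4.1 point the same way. Section 6.4.2 already plans sensitivity analyses of MAR, and Section 6 leaves full analysis details to the SAP.

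Much of this stands. The intent is clear, and the remedy restores a rule the protocol already contains. But the same section also states the option to leave, with nothing to override it. Sensitivity analyses cannot recover data never collected, and that commitment is attached to the continuous endpoints, not the lesion counts.

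Three stronger readings are tempting but unsupported:

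- *The secondary results will be biased in a known direction.* Size and sign depend on the split between relapses and new lesions, how the effect changes after the last infusion at Week 48, and how well a later DMT works. The documents give none of these.
- *The primary endpoint is undermined.* A patient who leaves at a centrally read new lesion, or at a confirmed relapse, already has the event. The exception is a patient who leaves on a local read that the central reader does not confirm: that patient has no event and is censored.
- *Section 4.4.1 contains an equally serious contradiction.* It says "After a confirmed clinical relapse, patients will be discontinued from the study and start commercially available DMT approved for MS" and then "Whether patients continue or discontinue the treatment based on the occurrence of a neurologic event consistent with MS is at the discretion" of physician and patient. The first concerns a confirmed relapse and the study; the second concerns a neurologic event and the treatment, and can be read as covering events not confirmed as relapse. This is a minor wording point.

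**Conclusion.** Both conflicts are in the current text and should be reconciled.

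The first puts Week 104 and 208 secondary data at risk in a way that depends on outcome and, at the planning rates, falls more on placebo. The counts rest on Section 6.1's rates and constant hazards. If radiologic events are more frequent, more patients are concerned; the background on RIS reports radiologic progression in two-thirds of patients, with a median of 2.7 years. How often physicians would use the option is unknown, so no bias estimate is offered.

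The exit-MRI conflict matters mostly for event-free dropouts. It reaches the primary endpoint, but only slightly: under one missed event in total at the planning rates.

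**What to change.** 1. Reconcile Sections 3.1 and 4.4.2 so that stopping study drug or starting a DMT after a radiologic event is separate from leaving study assessments. Assessments would continue as Section 4.4.2 already states, and treatment decisions would stay with the treating physician.
2. Reconcile footnotes c and r so that it is clear whether the early-termination MRI is obtained, including for patients who leave without an event.
3. State in Section 6.4.2 or the SAP the intercurrent-event strategy for DMT start in the secondary estimands, consistent with item 1.

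The two Section 4.4.1 sentences can be reconciled in the same amendment; nothing here says which is right.

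The cost is mainly wording, since the follow-up visits and scans are already in the schedule. A few patients would stay in visits they might otherwise have left, and some may decline. Data collected after DMT start would enter the secondary analyses, which is why item 3 is needed. The change is best made early, because data lost after an exit cannot be recovered.
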